3.2 Secondary Outcomes

The secondary outcomes of the study include the following:

1. **Take-up of mental health app.** This is measured in two ways: participants expressing interest in accessing a mental-healthcare app in the survey, and participants actually clicking a link to download the app.
2. **Demand for information about mental health.** This is measured in two ways: participants expressing interest in receiving more information about mental health, and participants actually clicking a link to access the information.
3. **Attendance of therapy sessions.** We will collect data from the administrative records of the counselling office on whether participants actually attended a therapy session, as well as the number of sessions attended.
4. **Other variables.** We will also report exploratory analyses and mechanism tests including: (i) whether participants report in the survey if they would consider seeking therapy in future; (ii) what steps they report they would take to take care of their mental health in future; (iii) reported motivating/inhibiting factors for taking up therapy and perceptions of therapy.

4 Empirical analysis

4.1 Main regression specification

Pooled treatment effects. Our main specification will be a linear regression of outcomes on the ‘pooled’ treatment assignment, separately for the screening treatment and rewards treatment. That is, define

$$\begin{aligned} \text{Pooled screen}_i &= \text{Screen}_i + \text{Screen and rewards}_i \\ \text{Pooled rewards}_i &= \text{Rewards}_i + \text{Screen and rewards}_i, \end{aligned}$$

where Screen_i is an indicator variable for i being assigned to the screening group, Rewards_i is an indicator variable for i being assigned to the rewards group, and $\text{Screen and rewards}_i$ is an indicator variable for i being assigned to the combined screening and rewards group.

To identify the effect of the pooled treatments on the outcome variables, we will run the following regression specification, separately for each pooled treatment and outcome variable:

$$Y_i = \alpha + \beta T_i + X_i' \lambda + \epsilon_i$$

where Y_i represents the outcomes for individual i described above, $T_i \in \{\text{Pooled screen}_i, \text{Pooled rewards}_i\}$ represents the pooled treatment indicators described above. X_i is a vector of controls consisting of the limited set of variables collected in the survey prior to treatment. This includes categories of PHQ-ADS scores (no risk, mild risk, or moderate-to-severe risk), whether participants report that their family would be supportive of seeking therapy, their current mood, their perception of their current and previous mental health and well-being, whether they have received mental health care in the past, interest in therapy at baseline, and a measure of their financial status.

Fully saturated model. For each outcome, we will also report a “saturated” regression which breaks up the effects by each of the treatment cells:

$$Y_i = \alpha + \beta_1 \text{Screen}_i + \beta_2 \text{Reward}_i + \beta_3 \text{Screen and Reward}_i + X_i' \lambda + \epsilon_i$$

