2.1 Sample Population

The experimental sample consists of college students at a college in Chennai who (i) are at least 18 years old, (ii) are present in the classrooms when we visit, and (iii) consent to participate in the study. We will attempt to visit all classrooms (i.e., all majors and years) over the course of the study. However, we rely on the college administration to make students available and scheduling constraints on the part of the college may keep us from visiting all classrooms. In addition, attendance rates on a given day are well below 100% (and as low as 50% during our scoping visits). Thus, the final experimental sample will be substantially smaller than the full college student population of approximately 3000.

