2.2 Treatments

Treatments are randomized at the individual level, stratified by categories of PHQ-ADS scores. Treatment status will be revealed via the survey administered through students' mobile phones. Participants will be randomized to four conditions:

1. **Control:** The control group will (a) watch a video introducing them to the mental health services available in the college, including introductory videos of the counselors, (b) have access to therapy at no cost for the duration of the study via their college counselors and additionally at SCARF, a mental health center in Chennai, and (c) be given links to book a therapy session or download a mental health app.
2. **Screening:** In addition to the interventions in the control group, students in the screening group will receive feedback on their PHQ-ADS score and recommendations based on that. In particular, they will be informed whether their responses to the PHQ-ADS questions fit in the standard risk categories of no, mild, moderate, or severe distress and corresponding recommendations for whether to make an appointment with a counselor/therapist.
3. **Rewards:** In addition to the interventions in the control group, students in the rewards group will be provided with a cash payment of Rs. 500 (USD 5.70 at market exchange rates) for attending a (first) therapy session.
4. **Screening and rewards:** Students in this group will receive both interventions, i.e., both the screening information and the reward described above.

For ethical reasons, participants with PHQ-ADS scores of 30 or above (indicating severe risk of depression and anxiety) in the non-screening treatment arms will also be informed of their scores at the end of the survey. For outcome variables measured within the survey, we will treat these participants as though they are part of the group to which they are randomly assigned. One outcome variable (completing the process to make an appointment for therapy) is measured after the conclusion of the participant survey. For this outcome variable, we will separately run regressions both including and excluding these individuals.

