4.2 Heterogeneity analysis

Heterogeneity by baseline mental health status. For our primary outcome and for selected secondary outcomes such as take-up of the app, we will analyze heterogeneity by baseline mental health status, as measured by the PHQ-ADS. This heterogeneity is policy-relevant, because policy-makers may especially value students at high risk of anxiety and depression receiving therapy. It also conceptually relates to our treatments, in that screening might be expected to cause more positive selection on symptoms of depression and anxiety while rewards have ambiguous selection effects.

The standard cutoffs in scores in the PHQ-ADS scale in the literature are 10-19 for mild symptoms, 20-29 for moderate symptoms, and 30 or higher for severe symptoms. We will combine the moderate and severe categories in our analysis, as only a small share of students are expected to show severe symptoms.

We will estimate the following regression:

$$Y_i = \alpha + \beta T_i + \gamma T_i \times \text{Mild}_i + \theta T_i \times \text{Moderate or Severe}_i + \lambda X'_i + \epsilon_i$$

for each of the pooled treatment indicators and outcome variables. The vector of controls X_i includes the indicator variables Mild_i and $\text{Moderate or Severe}_i$.

We will also run a model which interacts the treatments with a continuous measure of the PHQ-ADS score:

$$Y_i = \alpha + \beta T_i + \gamma T_i \times \text{PHQ-ADS}_i + \lambda X'_i + \epsilon_i$$

where X_i is the vector of controls now including the continuous measure of PHQ-ADS score.

Heterogeneity by other characteristics. As exploratory analyses, we will examine heterogeneity by other baseline characteristics, such as participants' financial status, their perception of their mental health status, and their major sources of stress.

Heterogeneity by other characteristics.

5 Funding and Human Subjects Review

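### The pooled regressions and the PHQ-ADS heterogeneity models omit the other randomised treatment; with proportional arms this leaves standard errors slightly wider than necessary.

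*Combined protocol and SAP*

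**What the plan says.** Section 2.2 describes a 2x2 design: "Participants will be randomized to four conditions", namely control, screening, rewards, and both. Randomisation is individual ("Treatments are randomized at the individual level, stratified by categories of PHQ-ADS scores"). No allocation ratio is given, and the plan does not say whether the arms are blocked to equal size within strata.

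Section 4.1 defines two pooled indicators, one for any screening and one for any rewards. For the main analysis, "we will run the following regression specification, separately for each pooled treatment and outcome variable". The only other terms come from X: "X_i is a vector of controls consisting of the limited set of variables collected in the survey prior to treatment". The other treatment's indicator is assigned, not surveyed, so it is not in X.

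Section 4.1 also plans, for each outcome, a saturated "regression which breaks up the effects by each of the treatment cells". That model does contain both treatments.

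Section 4.2 fits its category model "for each of the pooled treatment indicators and outcome variables", with one treatment, its interactions with Mild and Moderate or Severe, and X. The continuous version has one treatment, its product with the score, and X ("X_i is the vector of controls now including the continuous measure of PHQ-ADS score"). Neither contains the other treatment, and no saturated heterogeneity model is planned.

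**The concern.** In a factorial trial the second factor is a known, randomised source of outcome variation. Leaving it out puts that variation into the residual. If rewards move take-up a good deal, the screening coefficient pays for it with a wider interval and a weaker test. The screening-by-severity interactions in Section 4.2 pay as well, and interactions are estimated less precisely to begin with.

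The sample is limited from outside. Section 2.1 says "the final experimental sample will be substantially smaller than the full college student population of approximately 3000" and reports attendance as low as 50% on scoping visits. More students are hard to come by, whereas the assignment data are already held.

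There is a second, conditional issue. If the four cells were not proportional, screening status would be correlated with rewards status, and the one-factor coefficient would absorb part of the other treatment's effect. Entering both factors guards against that.

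**Working it through.** **Inputs.** The plan gives no target N, outcome rates, effect sizes or allocation ratio, so there is no figure of its own to reproduce. Assumed: N = 1500 (3000 students x 50% attendance), equal arms, and three sets of outcome rates. The standard-error ratios do not depend on N.

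**Main model, equal arms.** Let V = p(1 − p) at the overall mean rate p, let eS and eR be the factorial main effects, and let R² be the share of V explained by X.

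- One-factor residual variance for screening: V(1 − R²) − eS²/4.
- Adding the rewards indicator removes a further eR²/4.
- SE = 2·sqrt(residual variance / N).
- Share removed: s = (eR²/4) / [V(1 − R²) − eS²/4].
- Widening of the SE = 1/sqrt(1 − s) − 1. Equivalent extra students = N[1/(1 − s) − 1].

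Worked case, 5/8/20/25%, R² = 0: p = 0.145 and V = 0.123975. eS = (3 + 5)/2 = 4 points and eR = (15 + 17)/2 = 16 points. The one-factor residual is 0.123975 − 0.0004 = 0.123575, giving SE = 1.82 points. The two-factor residual is 0.123575 − 0.0064 = 0.117175, giving SE = 1.77 points. Then s = 0.0064/0.123575 = 0.0518 and the widening is 2.7%.

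| Rates, control/screening/rewards/both | eR (points) | s | Screening SE too wide, R² = 0 | Same, R² = 0.2 | Equivalent students (R² = 0) | Rewards SE too wide (R² = 0) |
|---|---|---|---|---|---|---|
| 5/8/10/14% | 5.5 | 0.0090 | 0.5% | 0.6% | 14 | 0.2% |
| 5/8/20/25% | 16 | 0.0518 | 2.7% | 3.4% | 82 | 0.2% |
| 5/7/35/40% | 31.5 | 0.1460 | 8.2% | 10.6% | 256 | 0.1% |

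For a 10-point effect of the omitted factor, ignoring the small effect of the factor kept in the model, the widening is 1/sqrt(1 − 0.0025/[p(1 − p)]) − 1: 0.5%, 1.0% and 1.4% at p = 50%, 15% and 10%.

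**Simulation** (4,000 runs, N = 1500, 5/8/20/25%, no covariates). With unblocked assignment the screening estimate has SD 1.83 points in the one-factor model and 1.77 in the two-factor model; mean SEs are 1.82 and 1.77, coverage 94.8% and 95.1%, and both average 4.0 points. With exactly balanced arms the point estimates are identical and only the mean reported SE differs, 1.82 against 1.77.

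**Section 4.2, screening model.** θ is the moderate-or-severe screening effect minus the no-risk one, so its variance is the sum of the two stratum variances. Assume a 50/30/20 severity split (750 and 300 students in the two strata that matter here), with rates of 3/4/13/14% for no risk and 10/18/34/48% for moderate or severe. Rewards then add 10 and 27 points.

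- One-factor: no risk (0.09·0.91 + 0.08·0.92)/375 = 0.000415; moderate or severe (0.33·0.67 + 0.22·0.78)/150 = 0.002618. SE = sqrt(0.003033) = 5.51 points.
- Two-factor, subtracting eR²/2 from each numerator: (0.1555 − 0.0050)/375 = 0.000401; (0.3927 − 0.03645)/150 = 0.002375. SE = sqrt(0.002776) = 5.27 points.
- Widening 4.5%.

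**Allocation.** The bias in the one-factor screening estimate is the reward effect times [P(rewards | screened) − P(rewards | not screened)]. This is zero under equal or proportional cells. Dropping students scoring 30 or above from both non-screening arms, as Section 2.2 plans for the appointment outcome, keeps equal arms proportional. Under a hypothetical 40/20/20/20 split at 5/8/20/25%, the one-factor screening estimate is (8 + 25)/2 − (0.4·5 + 0.2·20)/0.6 = 16.5 − 10.0 = 6.5 points, against 3.86 from the two-factor model. For rewards it is 22.5 − 6.0 = 16.5 against 15.86. At that split with N = 1500, a 20% control rate, no screening effect and a 10-point reward effect, the screening estimate is expected to read +1.7 points and a nominal 5% test rejects about 11% of the time.

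**The case against.** The strongest reply is that nothing here is an error. With proportional arms the one-factor regression is unbiased and its standard error is valid or conservative, so the choice is between two sound specifications. That stands, and it caps the importance of the point.

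Second, the saturated model largely covers Section 4.1. With equal arms, linear combinations of its coefficients recover the pooled effects with the two-factor standard errors (1.77 points at 5/8/20/25%). That is true, but the plan names the one-factor regressions as its main specification, does not plan those combinations, and has no saturated counterpart in Section 4.2.

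Third, the student equivalents can mislead. If arms are exactly balanced, the estimate itself does not become more precise; a conservative reported standard error is corrected. That also stands: the figures of 14, 82 and 256 describe interval width and test power, not always the true spread of the estimate. Intervals and tests are nevertheless what will be reported.

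Fourth, the larger figures need a large reward effect. The payment is tied to attending a first session, so for the app and information outcomes the gain may be nil. Fifth, the unequal split is invented; silence about the ratio is a reason to ask for it, not evidence of bias. Both are accepted.

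Last, changing the main model during data collection adds a second boundary to a plan that already promises a check restricted to data collected after posting. Keeping the one-factor regressions as a sensitivity analysis makes that cost small.

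**Conclusion.** The concern holds as a modest, optional improvement. The main pooled models and both PHQ-ADS models omit a randomised factor that the trial itself creates. If cells are equal or proportional and the omitted treatment has an effect, the reported standard errors are wider than needed. For the main screening coefficient this is about 1% or less for most reward effects up to 10 points, 2.7% at 16 points and 8.2% at about 30. For the rewards coefficient it is negligible. For the moderate-or-severe screening interaction it is 4.5% in the case worked above. If the other treatment has no effect, there is essentially no cost.

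All rates, the severity split and N are assumptions. Under non-proportional allocation the issue would be bias rather than width. Nothing in the plan points to that, but it cannot be ruled out until the ratio is stated.

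**What to change.** By dated amendment:

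- **Section 4.1.** Make the main model one regression per outcome: Y = α + β_S·Pooled screen + β_R·Pooled rewards + X′λ + ε. Keep the one-factor regressions as a sensitivity analysis.
- **Section 4.2.** Enter both pooled treatments, each with its own interactions with Mild and Moderate or Severe, or with the continuous score.
- **Section 2.2.** State the allocation ratio.
- **Saturated model.** Keep it. It supplies the screening-by-rewards interaction as β3 − β1 − β2. With equal arms, the pooled effects are (β1 + β3 − β2)/2 for screening and (β2 + β3 − β1)/2 for rewards. If arms are unequal, say which weighting is meant, because the two routes then differ (3.86 against 4.00 points for screening in the 40/20/20/20 example).

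The cost is one added term per main regression and the matching interactions in Section 4.2, with no new data. The amendment must be dated because recruitment began on 24 January 2025, before the plan's date of 12 February 2025.

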Using Financial Incentives and Screening to Increase Engagement with
Mental Health Services among College Students in Chennai, India
Pre-analysis plan

12 February 2025

1 Introduction

This study will evaluate the effectiveness of interventions to increase engagement with mental health services among a sample of college students in Chennai, India. We have partnered with an arts and science college for women in Chennai, where the study will be conducted. The sample will be recruited in person during college hours.

We will introduce the study to all students present in the classrooms at the time allotted by the college administration and obtain consent from those interested after screening them for age eligibility (between the ages of 18 and 30). Study participants will then complete a survey via a Qualtrics link using their cell phones. The survey will include questions about demographics, perceptions of their own mental health, mental health treatment history, and the PHQ-ADS, a standardized composite screening tool for depression and anxiety.

The experimental design is an RCT with 4 groups, randomized at the individual level. The investigators will measure interest in, and take-up of, psycho-therapy at the individual level. We will also collect data on other activities that capture engagement with mental health care, such as take-up of a cellphone app that provides tools to improve mental health, and seeking information about mental health.

2 Sample and Treatment

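### The main regressions adjust for PHQ-ADS only in three bands, although the full pre-treatment score could be added at almost no cost for a small possible gain in precision

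*Combined protocol and SAP*

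**What the plan says.** Section 4.1 describes the controls this way: "X_i is a vector of controls consisting of the limited set of variables collected in the survey prior to treatment". For PHQ-ADS, the list names "categories of PHQ-ADS scores (no risk, mild risk, or moderate-to-severe risk"). It goes on to current mood, family support, perceived current and past mental health, and "whether they have received mental health care in the past, interest in therapy at baseline, and a measure of their financial status".

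The bands come from the cutoffs in section 4.2: "10-19 for mild symptoms, 20-29 for moderate symptoms, and 30 or higher for severe symptoms". The two upper groups are merged there because few severe scores are expected.

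The instrument itself, described in the Introduction as "the PHQ-ADS, a standardized composite screening tool for depression and anxiety", is part of the survey. It must be scored before assignment, because section 2.2 says "Treatments are randomized at the individual level, stratified by categories of PHQ-ADS scores". That section does not say which categories are the strata. In describing the screening feedback it mentions four, saying that students are told whether their responses "fit in the standard risk categories of no, mild, moderate, or severe distress".

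The continuous score enters the controls in one place only, the continuous-interaction model of section 4.2: "where X_i is the vector of controls now including the continuous measure of PHQ-ADS score".

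**The concern.** Cutting a score into bands keeps the differences between bands and drops those within them. Under the three-band model a student scoring 20 and one scoring 40 count as the same, as do students at either end of the mild band. If higher scores within a band go with more interest in therapy or more appointments, that variation stays in the residual, and chance imbalance between arms within a band is not adjusted away.

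At stake is the precision of every regression in 4.1, including those for both primary outcomes (expressing interest in therapy and making an appointment). The validity of the comparison is not at stake. A secondary matter is analyst discretion: the covariate sentence in 4.1 is worded as inclusive, so it is not fully settled whether the score could be added later.

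**Working it through.** **No plan figure to reproduce.** The plan states no target sample size, power, outcome rate, score distribution or score-outcome correlation. It gives only a college population of about 3000, with a sample expected to be well below that. Apart from the cutoffs of 10 and 20, every input below is an assumption.

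**Step 1: how much of the score the bands keep.** Let η be the share of score variance captured by the three bands. Gamma-shaped scores were simulated (capped at 48) and cut at 10 and 20:

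| Assumed mean, SD | η |
|---|---|
| 8, 6 | 0.796 |
| 12, 8 | 0.818 |
| 15, 9 | 0.790 |
| 18, 9 | 0.737 |

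The bands therefore already hold about 74% to 82% of the variation in the score.

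**Step 2: effect on the standard error.** Suppose the outcome is linear in the score with correlation ρ. Then R² for the bands is ηρ². R² for bands plus score is ρ², because the bands add nothing once a truly linear score is in the model. The ratio of standard errors is √[(1 − ρ²)/(1 − ηρ²)].

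Worked at ρ = 0.3:
- η = 0.818: √(0.9100/0.9264) = 0.9911, a reduction of 0.89%.
- η = 0.737: √(0.9100/0.9337) = 0.9872, a reduction of 1.28%.

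| ρ | R² bands (η 0.818 / 0.737) | R² bands + score | Lower SE | Equivalent gain in N |
|---|---|---|---|---|
| 0.1 | 0.0082 / 0.0074 | 0.0100 | 0.09% / 0.13% | 0.18% / 0.27% |
| 0.2 | 0.0327 / 0.0295 | 0.0400 | 0.38% / 0.54% | 0.76% / 1.10% |
| 0.3 | 0.0736 / 0.0663 | 0.0900 | 0.89% / 1.28% | 1.80% / 2.60% |
| 0.4 | 0.1308 / 0.1179 | 0.1600 | 1.69% / 2.41% | 3.47% / 5.01% |
| 0.5 | 0.2044 / 0.1843 | 0.2500 | 2.91% / 4.11% | 6.08% / 8.76% |

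The range of 0.1% to 1.3% corresponds to ρ from 0.1 to 0.3. The last two rows show what a stronger relation would give; nothing in the plan supports or excludes them.

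**Step 3: a second route.** A simulation with a logistic outcome model fitted bands, then bands plus score. In one scenario R² rose from 0.0591 to 0.0832: √(0.9168/0.9409) = 0.987, a 1.3% lower standard error. In a weak scenario R² rose from 0.0107 to 0.0139: √(0.9861/0.9893) = 0.998, a 0.2% lower standard error. This agrees with Step 2.

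**Step 4: the other covariates.** Steps 2 and 3 leave them out. With one covariate overlapping the score (assumed latent correlation 0.5 to 0.7, outcome rates about 5% to 21%), adding the score cut the standard error by 0.1% to 1.0% where both predicted the outcome. It reached 1.3% to 2.6% only where the score carried all the prognostic information. Covariates unrelated to the score work the other way, but weakly: if they explain 15% of outcome variance, the ρ = 0.3 reductions become 1.06% and 1.52% for the same two values of η. Mood and perceived mental health plausibly overlap with PHQ-ADS, so shrinkage is the likelier direction.

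**Step 5: when the gain vanishes.** If outcome rates were 10%, 20% and 35% by band and flat within each, the bands would give R² of 0.036 to 0.054 and a linear score alone only 0.029 to 0.043. Replacing the bands would then lose precision. Adding the score to them would gain nothing.

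**Step 6: power.** Assume N = 1500 split 750/750, two-sided α = 0.05, outcome SD 0.4, η = 0.80, and an effect set for 80.0% power with bands. Adding the score under Step 2's linear relation gives 80.1% at ρ = 0.1, 80.8% at ρ = 0.3 and 82.5% at ρ = 0.5.

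**Step 7: cost.** One degree of freedom is about 1/N of the residual variance: 1/1000 = 0.1% at an assumed N of 1000, or about 0.05% of the standard error.

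**The case against.** The strongest reply is that this is a modelling preference. Adjusting for categories when randomisation is stratified on categories is standard and defensible. The gain needs the score to predict the outcome within bands, given mood, perceived mental health, past care and baseline interest in therapy, and no document figure shows that it does. All of this stands.

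Three stronger readings are tempting, and the documents do not support them:

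- *The treatment effect is biased.* Assignment is randomised within PHQ-ADS categories, so leaving out the continuous score affects precision only.
- *Sections 4.1 and 4.2 use inconsistent adjustment sets.* Each interaction model in 4.2 carries the main effect of its own moderator: band indicators for the banded model, the score for the continuous one. The main model has no such interaction, so the difference follows from model structure.
- *The severe share within the top band is left to chance.* This depends on the strata, which section 2.2 does not define. If severe is a stratum of its own, that share is balanced by design. If the strata are the three bands of 4.1, it is not.

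What does not stand is the inference that a step-shaped relation defeats the proposal. That argument counts against replacing the bands with a linear score. Adding the score to the bands cannot lower R², so the worst case is one spent degree of freedom.

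**Conclusion.** The point holds as a minor, optional refinement. The three-band adjustment in 4.1 leaves within-band information unused although the score is already in hand. The expected benefit is small: on Step 2's assumptions, a standard error lower by roughly 0.1% to 1.3%, probably towards the low end with the full covariate list, and zero if only the band matters. A larger gain would need a stronger correlation than 0.3, or a score carrying nearly all the prognostic information; the plan gives no basis for assuming either. The conclusions of the trial are unlikely to turn on this. A reader might infer that certain precision is being thrown away, but the gain is possible rather than assured.

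**What to change.** In section 4.1, define X_i to contain (a) indicators for the PHQ-ADS categories exactly as used to stratify randomisation, stating whether these are three or four, and (b) the continuous PHQ-ADS score, alongside the covariates already listed. Apply this to all primary and secondary regressions. Keep the category indicators, so that the stratification factor stays in the model.

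Recruitment began on 24 January 2025 and the plan is dated 12 February 2025, so record the change with a date, before outcome analysis. If outcomes have already been analysed, report the version with the score as a sensitivity analysis instead.

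The cost is a line of plan wording and one degree of freedom. No new data are needed.
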